11.4 Primary Objective Analysis

Change in diabetes-related distress in parents/caregivers of children who utilize the ACCU-CHEK® Connect Diabetes Management system compared to the change observed in the Control Group. Diabetes related distress will be measured via the PAID- C & T parent questionnaires which will be administered Pre and Post Study Participation.

A change in the total PAID-C & T parent score between pre and post study will be calculated and compared between groups utilizing with treatment group as the independent variable, and covariates such as baseline PAID, and child demographic and diabetes history variables.

Descriptive statistics for observed and change from baseline scores, and 2-sample t-tests will be presented at both 3 and 6 month visits. This analysis will be performed on the Full Analysis Set population.

11.5 Secondary Objective(s) Analysis

The following secondary objectives will be analyzed by comparing the Pre-Post changes in questionnaire scores from subjects utilizing the ACCU-CHEK® Connect Diabetes Management system with changes from those subjects in the Control Group. Pre, Post, and Change scores will be calculated for each group and summarized by descriptive statistics. The change scores will be compared between groups utilizing both ANCOVA methods described above, and with 2-sample t-tests. These analyses will be performed on both the FAS and the ITT populations.

- Change from baseline in PAID- C & T parent at 3 months in parents/caregivers.
- Change from baseline in diabetes-related family conflict in parents/caregivers as measured by DFCS questionnaires at 3 and 6 months

- Change from baseline in attitudes toward blood glucose monitoring in parents/caregivers as measured by BGMC-parent questionnaire at 3 and 6 months.
- Change from baseline in diabetes-related distress among school-age children as measured by the PAID- C & T child questionnaires at 3 and 6 months.
- Change from baseline in perceived family conflict among school-age children measured by the DFCS-youth questionnaire at 3 and 6 months.
- Change from baseline in affect toward blood glucose monitoring (BGM) among school-age children as measured by the BGMC-youth questionnaire at 3 and 6 months.
- Change from baseline in perceived family conflict in parent/caregiver as measured by DFCSparent questionnaire at 3 and 6 months.
- Changes from baseline in glycemic control at 3 and 6 months defined as:
 - o HbA1c
 - Percentage in Glucose Target Range
 - o Glycemic Variability
 - Hypoglycemia
- The secondary objectives of ease of use, satisfaction, and preference for using the ACCU-CHEK® Connect Diabetes Management System compared with previous systems will be analyzed by summarizing the end of study outcomes from the following participant groups within the intervention group:
 - o Parent
 - o Children
 - School staff
 - Healthcare Provider (s)

Each question from this Post Questionnaire will be summarized separately utilizing descriptive statistics of the numerical scale value of the question (mean, standard deviation, range and 95% CI), and the distribution of values (number and percent of respondents at each level of response). These analyses will be performed on both the FAS and the ITT populations

11.6 Safety Analysis

All AEs will be coded using the Medical Dictionary for Regulatory Activities (MedDRA). Only AEs occurring after the start of the ACCU-CHEK [®] Connect Online Diabetes Management System will be included in the AEs tables.

Summaries of incidence rates (frequencies and percentages) of individual AEs by MedDRA System Organ Class and Preferred Term will be prepared. Such summaries will be displayed for all AEs, AEs by maximum severity, AEs by strongest causality to study device (and any associated pump devices), and AEs leading to withdrawal of study device.

Deaths, other SAEs and AEs leading to withdrawal will be listed separately.

Episodes (numbers) of the following AEs will be summarized:

- Symptomatic hypoglycaemia
- Severe hypoglycaemia (SAEs)

Diabetic Ketoacidosis (SAEs)

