2.1 Study Design Overview

This is a prospective, interventional, multi-center, post-market, 6-months, cluster randomized study, conducted in the US. In order to maintain a true control group for comparison, the investigational sites will be randomly assigned to one of the following treatments:

- Interventional Group ACCU-CHEK® Connect Diabetes Management System
- Control Group Usual care: Continued use of subjects' current diabetes devices

[figure not shown]

Figure 1 Study Design

Between 150 - 200 children with diabetes will be included in the clinical study and the duration of participation is 6 months for each subject. A cluster of 10-20 children is expected to enroll at each investigational site.

All subjects recruited by an Interventional Site will be provided with an ACCU-CHEK[®] Connect DMS (and up to one additional meter to keep at school), trained in the system's use, and asked to use this system for the following 6 months.

All subjects recruited by the Control site will continue to use their current diabetes management system.

All parents/caregivers independently of the age of their child are also part of the study, and will complete questionnaires about diabetes related stress, system use and other aspects of diabetes.

Furthermore, the health care providers (investigators and study staff) as well as school staff will also be asked to assess their preference in comparison to previously used systems. In order to obtain data prior to study start self-monitored blood glucose (SMBG) data from all subjects will be downloaded at Baseline using Diasend – for the data transfer to the eCRF

During the study the Control sites will continue to download data using Diasend whereas data download at Interventional sites will be managed by ACCU-CHEK® Connect DMS.

Control sites will continue to use data analysis methods according to their current practice for making therapy decision throughout the study. No change in behavior should be introduced by the study in this group and therefore they will not use data downloads via Diasend for therapy decisions, if this is not currently their practice, but they might need to perform downloads via Diasend for eCRF transfer only.

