- Download SMBG data using existing site process and discuss SMBG download with patient and parent/caregivers and collaboratively agree on therapy changes (pharmacologic and/or behavioral) and modify SMBG regimen, if needed.
- Download current BG meter using Diasend for eCRF data
- Schedule appointment for week one phone call (Visit 2) and 3 months (Visit 3)
- Record number of days missed from work (parent/caregiver)/school (child with diabetes) that
 are diabetes related in previous 3 months and indicate reason (doctor appointments, illness or
 other.
- Discuss and record current prescribed therapy (pharmacologic and/or behavioral) and prescribed SMBG regimen.
- Record any adverse events (AEs) since last visit if not done immediately
- Record all relevant data in the eCRF

Intervention Sites, only

- Dispense ACCU-CHEK[®] Connect DMS and record serial number of BG meter(s)
- Dispense Smartphone to child/adolescent (if applicable)
- Set up ACCU-CHEK[®] Connect DMS for connectivity, portals & invitations
- Provide training in the use of the system
- register current operating system of smart phone with version number
- Dispense Call Center Card and instruct in reporting of malfunctions/complaints with ACCU-CHEK® devices

7.3 Visit 2 – Phone Call one week after Visit 1

Study procedures include the following assessments:

- Record any adverse events (AEs) since last visit, if this has not been done immediately
- Record malfunctions/complaints of any device, if any
- Intervention group: Follow-up with parents/caregivers and child with diabetes to identify issues/obstacles associated with system in use
- Record all relevant data in the eCRF

7.4 Visit 3 - 12 weeks after Visit 1

Study procedures include the following assessments:

- Record any malfunctions/complaints, of device as applicable
- Assess and record any new AE, if this has not been done immediately and/or changes to ongoing AE/SAEs since the previous visit.
- Download child's BG data and review
 - o Intervention Sites: review ACCU-CHEK Connect Diabetes Management data
 - Control Site(s) review usual care SMBG data
- Discuss SMBG download with patient and parent/caregivers and collaboratively agree on therapy changes (pharmacologic and/or behavioral) and modify SMBG regimen, if needed.
- Discuss any change in software, devices, or apps used to manage diabetes or monitor child w/diabetes remotely
- Collect height and weight

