7.8 Training of Subjects

In order to prepare subjects as well as their parents/caregivers for the study procedures, they will be trained at the Baseline Visit (Visit 1) in the following:

Intervention Group:

The children with diabetes as well as their parents/caregivers will be trained in the following:

- use and functionalities of the ACCU-CHEK® Connect DMS.
- reporting of malfunctions/complaints via the Call Center
- general study procedures

Control Group:

The children with diabetes as well as their parents/caregivers in this group will only be trained in general study procedures, as the children continue to use their previous diabetes management system.

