5.6 Safety Analyses

The patient incidence of adverse events will be summarized by intervention group, MedDRA System Organ Class and Preferred Term. Such summaries will be displayed for all AEs, AEs by maximum severity, AEs by strongest causality to study device (and any associated pump devices), and AEs leading to withdrawal of study device. A separate analysis of the patient incidence of symptomatic hypoglycemia, severe hypoglycemia (SAE), and diabetic ketoacidosis (SAE) will also be presented.

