Table 2.7.2.2	Exit Questionnaire: Usability Child with Diabetes ITT Population
Table 2.8.1.1	Exit Questionnaire: Satisfaction Parent/Caregiver of Child with Diabetes FAS Population
Table 2.8.1.2	Exit Questionnaire: Satisfaction Parent/Caregiver of Child with Diabetes ITT Population
Table 2.8.2.1	Exit Questionnaire: Satisfaction Child with Diabetes FAS Population

Roche Diabetes Care, Inc

Table No.	Title
Table 2.8.2.2	Exit Questionnaire: Satisfaction Child with Diabetes ITT Population
Table 2.9.1.1	End of Study Questionnaire: Preference Parent/Caregiver of Child with Diabetes FAS Population
Table 2.9.1.2	End of Study Questionnaire: Preference Parent/Caregiver of Child with Diabetes ITT Population
Table 2.9.2.1	End of Study Questionnaire: Preference Child with Diabetes FAS Population
Table 2.9.2.2	End of Study Questionnaire: Preference Child with Diabetes ITT Population
Table 2.10.1.1	School Nurse Questionnaire: Preference FAS Population
Table 2.10.1.2	School Nurse Questionnaire: Preference ITT Population
Table 2.10.2.1	School Nurse Questionnaire: Usability FAS Population
Table 2.10.2.2	School Nurse Questionnaire: Usability ITT Population
Table 2.10.3.1	School Nurse Questionnaire: Satisfaction FAS Population
Table 2.10.3.2	School Nurse Questionnaire: Satisfaction ITT Population
Table 2.11.1.1	HCP Questionnaire: Preference FAS Population
Table 2.11.1.2	HCP Questionnaire: Preference ITT Population
Table 2.11.2.1	HCP Questionnaire: Usability FAS Population
Table 2.11.2.2	HCP Questionnaire: Usability ITT Population
Table 2.11.3.1	HCP Questionnaire: Satisfaction HCP Eligibility Population
Table 3.1	Summary of All Adverse Events by MedDRA SOC and Preferred Term Safety Population

Roche Diabetes Care, Inc

Table No.	Title
Table 3.2.1	Summary of All Adverse Events by Maximum Severity Safety Population
Table 3.2.2	Summary of All Adverse Events by Strongest Causality to Study Device Safety Population
Table 3.2.3	Summary of All Adverse Events Leading to Withdrawal from the Study Safety Population
Table 3.3	Summary of Symptomatic Hypoglycemia, Severe Hypoglycemia and Diabetic Ketoacidosis Safety Population

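### The Protocol 11.6 start rule for the adverse event tables cannot be met by control subjects and conflicts with SAP 5.6, which applies no such rule

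*Protocol*

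**What the plan says.** Protocol 11.6 sets an inclusion rule for the AE tables: "Only AEs occurring after the start of the ACCU-CHEK [®] Connect Online Diabetes Management System will be included in the AEs tables". It gives no alternative start for controls. It then describes the output: "Summaries of incidence rates (frequencies and percentages) of individual AEs by MedDRA System Organ Class and Preferred Term will be prepared", with breakdowns by severity, by causality and by withdrawal of the device, plus episode counts for hypoglycaemia and ketoacidosis. It does not itself ask for a display by group. Deaths, other serious AEs and AEs leading to withdrawal are to be listed separately.

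SAP 5.6 covers the same summaries and adds the group dimension: "The patient incidence of adverse events will be summarized by intervention group, MedDRA System Organ Class and Preferred Term". It contains no onset rule. In SAP section 6, Table 3.1 is titled "Summary of All Adverse Events by MedDRA SOC and Preferred Term Safety Population", Tables 3.2.1 to 3.2.3 are likewise headed as covering all AEs, and Table 3.3 is "Summary of Symptomatic Hypoglycemia, Severe Hypoglycemia and Diabetic Ketoacidosis Safety Population". None carries a time window.

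On exposure, Protocol 2.1 says that control subjects "will continue to use their current diabetes management system". Protocol 7.2 places the set-up of "Connect DMS for connectivity, portals & invitations" among the Visit 1 tasks for intervention sites only. Protocol 7.8 says that control families "will only be trained in general study procedures, as the children continue to use their previous diabetes management system".

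**The concern.** A counting start has to exist for every subject who is counted. Here it is an event that happens in one arm only. AEs are nevertheless recorded in both arms, and Protocol 11.2 puts all subjects in the safety population.

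At stake is the tabular comparison of safety between the arms, including Table 3.3 on symptomatic hypoglycaemia, severe hypoglycaemia and ketoacidosis. A control column emptied by a filter would look like an absence of events, and the device arm would appear worse than usual care for a reason unrelated to the device. The other course, counting control AEs, means departing from a written Protocol rule without a stated replacement. That choice is better settled before the data are seen.

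**Working it through.** There is no planned figure to reproduce. The check compares the texts and counts the outputs affected.

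1. **Does any control subject have the qualifying start?** In the Schedule of Assessments (Protocol and SAP 2.1.3), dispensing, training and set-up of Connect carry the intervention-only footnote. Protocol 2.1 and 7.8 keep controls on their existing system. Protocol 7.12 mentions starting Connect only as an option once participation has ended. So no control subject reaches the qualifying event under the study.

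2. **Are controls otherwise in the safety analysis?** The AE/SAE row of the Schedule has no group footnote and starts at Visit 1. The Protocol 11.2 safety population is everyone. The SAP 4.5 safety population requires consent or assent and at least one day of participation, with no restriction by arm. So controls are included.

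3. **Does the SAP replace the rule?** SAP 3.1 and 3.3 define baseline and study day from Visit 1 but do not link AE counting to either. The same-day assumption in SAP 3.5.2.1 concerns glucose readings from Connect users. SAP 5.6 gives neither a reference date nor a treatment-emergent definition. So the Protocol rule is neither repeated nor replaced.

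4. **What does each reading produce?**

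| Reading | Intervention AEs tabulated | Control AEs tabulated |
|---|---|---|
| Protocol 11.6 applied literally | Those after Connect Online starts | None |
| SAP 5.6 and section 6 alone | All recorded, from Visit 1 | All recorded, from Visit 1 |
| Protocol filter carried into the SAP's by-group tables | Those after Connect Online starts | Zero by construction |

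5. **How many outputs are exposed?** SAP tables: 3.1 (1) + 3.2.1 to 3.2.3 (3) + 3.3 (1) = 5. SAP AE listings: 15.1 (1) + 15.2.1 to 15.2.2 (2) + 15.3.1 to 15.3.4 (4) = 7. None of the seven is exposed, because the Protocol sentence restricts tables only. The between-arm analysis of the percentage of readings below 70 mg/dl (SAP 3.5.2.2 and 5.5.2) comes from meter data and is also untouched.

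**The case against.** The strongest reply is that the SAP works on its own terms. It summarises all AEs in the safety population, recording begins at Visit 1 in both arms, and Visit 1 is Day 1. A programmer following only the SAP would count control events without difficulty. This stands. A reader might infer that the plan leaves controls with no usable counting start at all, and the documents do not support that. What is missing is a written onset window and a reconciliation with the Protocol.

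A second reply is that the empty control column needs a mixture of the documents: the Protocol has the filter but no by-group display, and the SAP has the by-group display but no filter. A milder reading is that the sentence was meant to exclude intervention events before device start, and an analyst would notice an emptied column. This also stands as far as it goes. A reader might infer that the plan will report zero control AEs. That cannot be concluded, because the output templates are in a separate document that is not available here. But the sentence as written has no such limitation, and Protocol section 11 does not say that SAP silence cancels a Protocol rule.

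A third tempting inference is that filtered tables would contradict the listings. They would differ in scope, which is not a contradiction. Serious control events would remain visible in the listings under either document.

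Finally, the SAP's phrase about intervention group could be read as the intervention arm alone. The natural meaning is by treatment group. On the narrower reading, control AEs would not be tabulated at all, which is no better.

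**Conclusion.** The point holds as a wrong stated rule in Protocol 11.6 that SAP 5.6 does not reconcile. Literal use of the rule drops all control AEs from the tables; use of the SAP alone drops none. Which would be produced cannot be settled from these two documents.

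Importance is low to moderate. The exposure is five safety tables, with collection and listings intact, and no size in events or percentages can be given. The conclusion assumes that controls do not start Connect during participation, as the Protocol plans, and that the SAP's group display means both randomised groups. The correction is worth making because it costs almost nothing and removes a choice that would otherwise be made after the data are in hand.

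**What to change.** Replace the Protocol 11.6 sentence, and put the same rule in SAP 5.6:

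*AEs with onset on or after Visit 1 (Day 1) through Visit 4 or early withdrawal are included in the AE tables for both groups, by randomised group.*

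Visit 1 is already the SAP baseline date for both arms. The window should close at Visit 4 or withdrawal rather than at last contact. Under Protocol 7.6 and 9.5, the follow-up call happens only for AEs still ongoing at Visit 4 and records only changes to them, so a last-contact limit would make the window depend on AE status.

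The downside is small: same-day intervention events before device set-up at Visit 1 may be counted. An alternative is to keep device start for the intervention arm and name Visit 1 for controls. This avoids that effect but gives the arms slightly different starts on Day 1.

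The cost is one sentence in each document, IRB submission of the Protocol change under Protocol 12.7, and a check that the separate output templates follow the same rule. No new data are needed: AEs and the Visit 1 date are already collected in both arms.

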11.7 Interim Analysis

No interim analysis will be conducted on the primary objective. Nevertheless a "data pull" analysis will be conducted at a suitable timepoint.

12 Ethical and Legal Considerations

12.1 Statement of Compliance

The study will be performed in accordance with the principles stated in the current version of World Medical Association's Declaration of Helsinki "Recommendations Guiding Physicians in Biomedical Research Involving Human Subjects", that are consistent with the principles outlined in the ICH Guideline on GCP where it applies to medical devices and the applicable national regulations for medical device law and applicable ordinances, FDA 21 CFR Parts 11, 50, 54, 56, 803, 812, 814 and 820.30, as applicable in each participating country.

12.2 Subject Informed Consent

It is the responsibility of the Investigator, or a person designated by the Investigator (if acceptable by local regulations), to obtain written Subject informed consent – before any study procedures – from each subject considering participation in this study, after adequate explanation of the aims, methods, anticipated benefits, and potential hazards of the study – orally as well as presented in the written Subject Informed Consent.

The Investigator or designee (if applicable) must also explain that the subject is completely free to refuse to enter the study or to withdraw from the study at any time, for any reason and could return to standard care.

The Investigator or authorized staff must document the date of each subject's informed consent in the respective eCRF.

If any new safety information results in significant changes in the risk/benefit assessment, the Informed Consent Form should be reviewed, updated and re-submitted to the IRB for approval.

Subjects already participating in the study should be informed of the new information, and asked to give their written inform consent to continue in the study.

New subjects shall only receive the updated documents.

All subjects will be given a copy of the signed Subject Informed Consent Form(s).

12.3 Confidentiality of Study Documents and Subject Records

The Investigator must assure that subjects' anonymity will be maintained and that their identities are protected from unauthorized parties. On the eCRFs or other documents submitted to the Sponsor, subjects should not be identified by their names, but by a unique study identification code, i.e. Subject ID (Number).

The Investigator will keep a **Subject Screening and Enrolment Log** linking study identification codes, and subject contact information. The Investigator will maintain these study documents e.g. subjects' written inform consent forms, in strict confidence and as part of the Investigator's Site File.

Any data obtained from subjects participating in the study may be used to build case studies for educational purposes and all identifying data will be completely removed or blacked-out for these purposes.

12.4 Data Protection

The subject and their parent/caregivers will be informed of their right of access, objection and correction of the data recorded during this study, and that this right may be exercised at any time through his/her physician.

Information relating to participating physicians will be declared and the physicians will be informed – within the framework of their agreement – of their right to access, object to and correct this information.

12.5 Institutional Review Board (IRB)

This protocol and any accompanying material provided to the subject (such as subject information sheets or descriptions of the study used to obtain informed consent) as well as any advertising used or compensation given to the subject, will be submitted by the Investigator to an IRB. Approval from the committee must be obtained before starting the study, and should be documented in a letter to the Investigator specifying the date on which the committee met and granted the approval. Any modifications made to the protocol after receipt of the IRB approval must be re-submitted by the Investigator to the Committee in accordance with local procedures and regulatory requirements.

